Clinical Trial Protocol: IT-004-401

Study Title: A prospective, Phase 4, open label, multi-center study of the

clinical and microbiologic efficacy of ciprofloxacin for the treatment of uncomplicated urinary tract infections in adult

women.

Study Number: IT-004-401

Study Phase: Phase 4

Product Name: Ciprofloxacin

Indication: Uncomplicated urinary tract infection

Investigators: Multicenter

Sponsor: Iterum Therapeutics US Limited

Sponsor Contact: [name].

Sponsor's Legal Iterum Therapeutics US Limited **Representative:** [name]

[name]

Medical Monitor: [name].

Office: [contact]

Email: [contact]

Pharmacovigilance Iterum Therapeutics US Limited

Pharmacovigilance

Contact

[name].

Office: [contact] [contact]

Email: [contact]

Date	
Original FINAL Protocol	September 29, 2017

Confidentiality Statement

This document is strictly confidential. It was developed by Iterum Therapeutics US Limited and should not be disclosed to a third party, with the exception of regulatory agencies and study audit personnel. Reproduction, modification or adaptation, in part or in total, is strictly forbidden without prior written approval by Iterum Therapeutics US Limited.

Throughout this document, symbols indicating proprietary names (®, TM) are not displayed. The appearance of product names without these symbols does not imply that these names are not protected.

Confidential Page 1 of 60

Clinical Trial Protocol: IT-004-401

SYNOPSIS

Sponsor:

Iterum Therapeutics US Limited

Name of Finished Product:

Ciprofloxacin

Study Title:

A prospective, Phase 4, open label, multi-center study of the clinical and microbiologic efficacy of ciprofloxacin for the treatment of uncomplicated urinary tract infections in adult women.

Study Number:

IT-004-401

Study Phase: Phase 4

Primary Objective(s):

To evaluate the clinical and microbiologic response of patients with a uUTI treated with ciprofloxacin.

Secondary Objective(s):

To evaluate the validity of specific tests found on the urine dipstick as a screening tool to identify symptomatic patients with a positive urine culture, defined as growth of $\geq 10^5$ CFU/mL of a uropathogen at baseline.

Study Design:

This prospective, Phase 4, open label, multi-center study documents the clinical and microbiologic response of adult women patients with uUTI treated empirically with ciprofloxacin. Approximately 250 adult women with uUTI will receive oral ciprofloxacin 250 mg twice daily for 3 days.

The primary outcome measure for efficacy evaluation will be the overall response on Day 12 (+/- 1 day). For the primary efficacy evaluation, these percentages will be based on a microbiologic-modified intent to treat population (m-MITT). The m-

MITT population will be comprised of all patients who received at least one dose of ciprofloxacin and had $\geq 10^5$ CFU/mL of a baseline pathogen isolated from a urine culture specimen taken at baseline, prior to initiation of ciprofloxacin therapy.

Study Population:

A total of approximately 250 patients are planned.

Inclusion Criteria:

- 1. Female patients ≥18 years of age with more than 24 hours of urinary symptoms attributable to a UTI
- 2. Two of the following signs and symptoms of uUTI: urinary frequency, urinary urgency, pain or burning on micturition, suprapubic pain, gross hematuria
- 3. A mid-stream urine specimen collected for the purpose of diagnosing a UTI with:
 - a. a dipstick analysis positive for nitrite AND
 - b. a dipstick analysis positive for leukocyte esterase
- 4. Has given written informed consent to participate in the study prior to Screening/Baseline (D1)

Exclusion Criteria:

- 1. Presence of signs and symptoms suggestive of acute pyelonephritis defined as: fever (temperature > 38° Celsius), chills, costovertebral angle tenderness, flank pain, nausea and/or vomiting
- 2. Receipt of prior effective antibacterial drug therapy for uUTI for the presenting illness unless the recovered pathogen demonstrates resistance to the initial antibiotic and clinical symptoms persist

Clinical Trial Protocol: IT-004-401

- 3. Concurrent use of non-study antibacterial drug therapy that would have a potential effect on outcome evaluations in patients with uUTI
- 4. Patients with ileal loops or urinary stoma
- 5. Patients with an indwelling urinary catheter in the previous 30 days
- 6. Patients with paraplegia
- 7. Patients who are likely to receive ongoing antibacterial drug prophylaxis after treatment of uUTI (e.g., patients with vesico-ureteral reflux)
- 8. Any history of trauma to the pelvis or urinary tract
- 9. Patient's urine culture results, if available at study entry, identify more than 2 microorganisms regardless of colony count or a potential fungal pathogen
- 10. Patient's urine culture results, if available at study entry, identifies causative uropathogen for the presenting illness to be resistant to ciprofloxacin
- 11. Patient has severe chronic kidney disease, or is receiving hemodialysis, or peritoneal dialysis or had a renal transplant
- 12. Patient is known to have severe neutropenia
- 13. Patient is known to be pregnant
- 14. Patients with uncontrolled diabetes mellitus
- 15. Patients with a known history of myasthenia gravis
- 16. Patients who require concomitant administration of tizanidine
- 17. Patients with a history of allergy to quinolones
- 18. Patient is considered unlikely to survive the study period or has a rapidly progressive or terminal illness, including septic shock, associated with a high risk of mortality

Test Product, Dose, and Mode of Administration:

Patients will receive ciprofloxacin 250 mg, to be taken by mouth twice daily for 3 days.

Formulation and Packaging:

The site Investigator or designee will provide the patient with either a pharmacy prescription or a supply for a 3 day (250 mg BID) course of generic ciprofloxacin for the treatment of their uUTI. The generic ciprofloxacin will be supplied by a local pharmacy, in the form of a filled prescription, that includes 6- 250 mg tablets of ciprofloxacin.

Preparation and Dispensing:

All generic ciprofloxacin will be prepared and provided to the patient via a prescribing pharmacy prescription, or, provided by the Investigator or designee.

Administration:

The patient will receive one 3-day treatment course of generic ciprofloxacin, with instructions to take one tablet or capsule of oral ciprofloxacin 250 mg twice daily beginning day 1 through 3 (+ 1 day).

In the event a patient's first dose is taken in the PM on Day 1, the patient will be expected to take an AM dose on Day 4 to receive the 6 doses of ciprofloxacin, and the EOT visit will occur on day 4 instead of day 3.

Safety Assessments

Safety will be assessed by means of collection of adverse events. Adverse events will be collected at every visit, beginning from the signing of Informed Consent.

Efficacy Assessments:

The assessment of clinical response includes a review of the following symptoms: urinary frequency, urinary urgency, pain or burning on micturition, suprapubic pain and gross hematuria.

Microbiologic response assessments will be made based on quantitative cultures performed on collected urine specimens.

Statistical Methods:

General Statistical Considerations:

Descriptive statistics, including the numbers and percentages for categorical variables, and the numbers, means, standard deviations, medians, minimums, and maximums for continuous variables will be provided. Comparisons will be made between response rates for patients with infection due to ciprofloxacin-susceptible and ciprofloxacin-non-susceptible isolates. Exploratory analyses may also be performed. Listings of individual patient's data will be produced.

Efficacy Analyses:

The study is designed to determine the clinical and microbiologic response of patients with a uUTI, due to ciprofloxacin-sensitive and ciprofloxacin-non-susceptible isolates, treated with ciprofloxacin for the outcome measure of overall response (combined clinical and microbiologic response) at Day 12 (+/- 1 day).

A patient will be defined as a responder if the following criteria are met:

- The patient is alive
- The patient has received no rescue therapy for uUTI
 - If an antibiotic active against the urinary tract pathogen is given for other reasons, then the patient will be considered indeterminate, and analyzed as a non-responder for uUTI
- The patient has resolution of the symptoms of uUTI present at trial entry and no new uUTI symptoms
- Urine culture taken on Day 12 (+/- 1 day) demonstrates <10³ CFU/mL of the baseline uropathogen

All other patients will be considered non-responders. If data are unavailable to determine if the patient is a responder or non-responder, the patient will be considered an indeterminate response.

The number and percentage of responders, non-responders and indeterminates will be determined. Descriptive statistics, including the numbers and percentages for categorical variables, and the numbers, means, standard deviations, medians, minimums, and maximums for continuous variables will be provided. In addition to the randomized m-MITT population, additional analyses will be performed in the subset of patients with ciprofloxacin-susceptible organisms at baseline and in

Clinical Trial Protocol: IT-004-401

those with ciprofloxacin-non-susceptible organisms at baseline. Exploratory analyses may also be performed. Listings of individual patient's data will be produced. A comprehensive Statistical Analysis Plan (SAP) will be finalized prior to the database lock.

The number and percentage of patients with a microbiologic success at the Day 12 (+/-1 day) visit will be determined. The validity of the urine dipstick as a screening tool to identify patients with a positive urine culture will be evaluated by calculating the percentage of patients with both a positive nitrite test and a positive test for pyuria on dipstick/urinalysis, who have $\geq 10^5$ CFU/ml of a uropathogen isolated from urine culture. Safety analyses will be conducted in all patients who receive any amount of ciprofloxacin. Safety will be assessed through summaries of AEs.

Date of Original Approved Protocol: September 29, 2017

Date of Most Recent Protocol Amendment (if applicable): March 27, 2018

TABLE OF CONTENTS

SYN	NOPSIS	2
LIST	T OF APPENDICES	13
LIST	T OF ABBREVIATIONS AND DEFINITIONS OF TERMS	14
1	INTRODUCTION	17
1	1.1 Indication	17
1	1.2 Background and Rationale	17
	1.2.1 Rationale for Study	17
	1.2.2 Dose Rationale	18
2	STUDY OBJECTIVES	18
2	2.1 Objectives	18
3	STUDY DESIGN	19
3	3.1 Investigational Study Medications	19
3	3.2 Adjunctive Systemic Antibiotics	19
3	3.3 Additional, Non-Study Therapy Antibiotics	20
4	STUDY POPULATION SELECTION	20
4	4.1 Inclusion Criteria	20
4	4.2 Exclusion Criteria	21
4	4.3 Enrollment Criteria	22
4	4.4 Women of Child-Bearing Potential	22
5	STUDY TREATMENTS	23
5	5.1 Allocation to Treatment	23
5	5.2 Drug Supplies	23
	5.2.1 Formulation and Packaging	23

	5.2.2	Preparation and Dispensing	24
	5.2.3	Compliance	24
	5.3 Dr	ug Storage and Drug Accountability	24
	5.4 Me	edication(s), Adjunctive Therapy and Non-drug Therapy	25
	5.4.1	Concomitant Medications	25
	5.4.2	Concomitant Antibacterial Medications	25
	5.4.3	Non-drug Adjunctive Therapy	25
6	STUDY	PROCEDURES	26
	6.1 Sci	reening (Day 1)	26
	6.2 Tre	eatment Period	26
	6.2.1	Baseline (Day 1)	26
	6.2.2	End Of Treatment (EOT) Day 3 or 4 (+1 day)	27
	6.3 Fo	llow-up Period	27
	6.3.1	Test of Cure (TOC) Day 12 (+/- 1 day)	27
	6.3.2	Post Test of Cure (TOC) Day 21 (+/- 3 days)	28
	6.4 Pat	tient Withdrawal from Treatment or Study	28
7	ASSESS	MENTS	28
	7.1 Sa	fety	28
	7.1.1	Clinical Laboratory Assays	28
	7.2 Eff	ficacy	29
	7.2.1	Overall Response	29
	7.2.2	Microbiologic	29
	7.2.3	Investigator-Determined Clinical Response	30
	7.2.4	Other Assessments	31

8	ADV	ERSE EVENT REPORTING	31
	8.1	Adverse Events	31
	8.2	Reporting Period.	31
	8.3	Definition of an AE	32
	8.4	Abnormal Test Findings	33
	8.5	SAEs	33
	8.6	Hospitalization	34
	8.7	Severity Assessment	35

GMP Good Manufacturing Practice

HIV Human Immunodeficiency Virus

HPF High Power Field

hs-CRP High-sensitivity C-reactive Protein

ICH International Conference on Harmonisation

ICF Informed Consent Form

IRB/IEC Institutional Review Board /Independent Ethics Committee

ITT Intent-to-Treat

IUD Intrauterine Device

IV Intravenous

IWRS Interactive Web Randomization System

LDH Lactate Dehydrogenase

LTFU Lost to Follow-Up

ME Microbiologically Evaluable

MIC Minimal Inhibitory Concentration

MITT Modified ITT (MITT)

mMITT Micro-MITT (mMITT)

NI Non-inferior

PK Pharmacokinetic

PK/PD Pharmacokinetic / Pharmacodynamic

SAE Serious Adverse Event

SAP Statistical Analysis Plan

TOC Test of Cure

T_{max} Time to maximum concentration

uUTI Uncomplicated urinary tract infection

WBC White Blood Cell

1 INTRODUCTION

1.1 Indication

Ciprofloxacin is being studied for the treatment of the following indications:

- Uncomplicated urinary tract infections

1.2 Background and Rationale

1.2.1 Rationale for Study

β-lactam antimicrobials are widely recognized for their efficacy and low toxicity and form the cornerstone of therapy for the treatment of infections caused by gram-positive and gram-negative bacteria. However, extensive use of \(\beta \)-lactams during the past 50 years has resulted in the development of microbial resistance to these agents among clinically important bacteria. This resistance commonly takes the form of \(\beta\)-lactamase production, development of porins or alterations in penicillin-binding proteins (PBPs). Such mechanisms have reduced the clinical utility of frequently prescribed B-lactams such as amoxicillin, amoxicillin plus clavulanate (a Blactamase inhibitor), and cephalosporins. For *Escherichia coli*, ampicillin resistance has risen to \geq 50% in high-risk populations, and resistance to third generation cephalosporins is now being seen in certain areas. Furthermore, the prevalence of infections caused by extended-spectrum β-lactamase (ESBL) producing Enterobacteriaceae has been increasing worldwide. An analysis of data reported from 2011 to 2014 to the National Healthcare Safety Network performed by the Centers for Disease Control in March 2016 revealed that the proportion of E. coli resistant to extended-spectrum cephalosporins causing hospital-acquired infection was 13.4% nationally, with rates as high as 24% reported in some Northeastern, Southern and Western states. The same analysis also demonstrated that over a third of E. coli isolates in 2014 were resistant to fluoroquinolones. Data reported by the European Antimicrobial Resistance Surveillance Network (EARS-NET) in Europe demonstrate that the prevalence of fluoroquinolone resistant E. coli and E. coli resistant to third-generation cephalosporins is > 25% and E. coli resistant to third generation cephalosporins, aminoglycosides and fluoroguinolones has increased to >10% in some southern and eastern European countries. Oral antibiotic treatment options are extremely limited for patients with these infections, resulting in lengthy hospital stays to facilitate administration of intravenous antibiotics, even for those with uncomplicated infections. The currently available oral antibiotics with activity against ESBL

producing organisms include nitrofurantoin, fosfomycin, fluoroquinolones and trimethoprim-sulfamethoxazole. Nitrofurantoin and fosfomycin are only approved for the treatment of uncomplicated urinary tract infections in the United States, have rising rates of resistance and are associated with inferior efficacy [Munoz-Davila 2014; Schito 2009]. Resistance to trimethoprim-sulfamethoxazole is uniformly above 20% in the US. Increasing prevalence of resistance to fluoroquinolones and their propensity to cause collateral damage resulted in relegation of fluoroquinolones to second-line therapy by the Infectious Disease Society of America (IDSA) for UTI [Gupta 2011]. Even with these limitations, almost two-thirds of patients with a uUTI receive therapy with a fluoroquinolone antibiotic. Furthermore, there is a percentage of uUTI patients treated with a fluoroquinolone who respond to therapy despite predicted failure based upon the results of in vitro susceptibility testing. The reason for this is likely multifactorial, including PK/PD relationships (i.e., concentration and duration of drug at the site of infection) and host factors. The proportion of patients with infection due to fluoroquinolone resistant pathogens who have clinical or bacteriological response to fluoroquinolone therapy has not been well studied, and most studies which have evaluated this issue have done so as part of a secondary analysis of a UTI treatment trial.

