9 DATA ANALYSIS/STATISTICAL METHODS

9.1 Sample Size Determination

The study is designed to determine the clinical and microbiologic efficacy of ciprofloxacin for adult female patients with uUTI, due to either a ciprofloxacin susceptible or non-susceptible organism. Two-hundred fifty (250) symptomatic patients will be enrolled with the expectation that there will be no screen failures. Of the 250 enrolled patients, we expect 50 will not have a positive urine culture for $\geq 10^5$ CFU/mL of a uropathogen at baseline. Of the 250 enrolled patients, we expect 40 will have a uUTI due to a ciprofloxacin non-susceptible organism.

Patients who withdraw prior to initial dose, will be replaced to ensure all 250 patients have received at least a single-dose of ciprofloxacin.

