9.5.1.1 Additional Analyses of the Primary Efficacy Outcome

In addition to the overall response rate, response rates for patients infected by ciprofloxacin susceptible and non-susceptible organism will be evaluated.

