- Overall response at Day 12 (+/- 1 day) (TOC) in the ITT, CE-TOC and ME-TOC population (m-MITT is used with the primary endpoint)
- Overall response, microbiologic response, clinical response and investigator response at the EOT and TOC visits by baseline pathogen (key pathogens) in the m-MITT and ME populations
- Overall response, microbiologic response and clinical response at the EOT and TOC visits by baseline ESBL in the m-MITT and ME populations
- Distribution of pathogens by culture concentration at EOT and TOC in the m-MITT, ME-EOT and ME-TOC populations

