6.4 Handling of Culture Data from Central and Local Laboratory

Culture data from both central lab (IHMA) and local lab at Baseline (no post-baseline for central lab) will be handled as outlined below:

- All the culture results from central and local labs are merged by subject id.
- Final pathogen, susceptibility (to Ciprofloxacin) and extended-spectrum beta-lactamases (ESBL) status at baseline will be determined in the following order as follows,
 - 1. For all uropathogen (Appendix 3) central records with concentration of $\geq 10^5$ CFU/mL then central lab pathogen, susceptibility and ESBL (ceftriaxone > 1 as positive) status is considered as final results.
 - 2. For all other central lab records with concentration $< 10^5$ CFU/mL or contaminated sample or 'no growth', if their local lab records have a uropathogen with concentration of $\ge 10^5$ CFU/mL then local pathogen, susceptibility and ESBL status is considered as final results.
 - 3. If both statement 1 and statement 2 do not apply, then central results are considered as final results.

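### Ciprofloxacin activity enters the response analysis at most as susceptible versus non-susceptible, with no stated cut-off and no table by baseline ciprofloxacin MIC

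*Protocol*

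**What the plan says.** **Purpose.** Protocol 1.2.1 notes that some women treated with a fluoroquinolone "respond to therapy despite predicted failure based upon the results of in vitro susceptibility testing". It suggests several causes, "including PK/PD relationships (i.e., concentration and duration of drug at the site of infection) and host factors". The gap it names is the proportion of infections with fluoroquinolone-resistant pathogens that respond clinically or bacteriologically. The primary objective (Protocol 2.1, SAP 3.1) is to evaluate response.

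**Planned split by ciprofloxacin activity.** Protocol 9.5.1.1 says "response rates for patients infected by ciprofloxacin susceptible and non-susceptible organism will be evaluated", and Protocol 9.3 plans a comparison of the same two groups.

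**SAP efficacy tables.** SAP 5.3 lists response by key baseline pathogen, and also "Overall response, microbiologic response and clinical response at the EOT and TOC visits by baseline ESBL in the m-MITT and ME populations". SAP 5.1.1, 5.3 and 7.6 list no response table by ciprofloxacin susceptibility. SAP 7.1 uses the susceptibility classes, but only for counts of patients in each analysis population. SAP 8, which records departures from the protocol, does not mention the difference.

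**Source of the label.** Under the first rule of SAP 6.4, for central records with a uropathogen at the qualifying count, "central lab pathogen, susceptibility and ESBL (ceftriaxone > 1 as positive) status is considered as final results". Under the second rule, where the central sample is below that count, contaminated or without growth, and the local laboratory has a qualifying uropathogen, the local pathogen, susceptibility and ESBL status are used. A threshold is given for ceftriaxone and none for ciprofloxacin.

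**MIC.** Protocol 9.5.3 has a microbiologic category for persistence with a rising MIC. The microbiologic definitions in SAP 5.3 leave it out. No table, subgroup or listing in either document shows response by baseline ciprofloxacin MIC.

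**The concern.** The rationale concerns resistant organisms and offers drug exposure at the site of infection as one reason why they may still respond. If that reason is right, response could differ between isolates just above a susceptibility cut-off and isolates far above it. The analysed class, non-susceptible, pools both. Without a stated cut-off or any display of MICs, a reader cannot tell which organisms the rate describes, cannot separate resistant from merely non-susceptible isolates, and cannot carry the rate over to a population with a different mix.

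Two features of the plan make this worse. The label can come from two sources with no stated common threshold. And the SAP commits to response tables by a ceftriaxone-based marker while committing to none by activity of the study drug, not even the two-way split that the protocol promised.

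**Working it through.** **1. The plan's own figures.** Protocol 9.1 and SAP 6.1 enrol 250 women. Of these "we expect 50 will not have a positive urine culture for" a uropathogen at the qualifying count, and "we expect 40 will have a uUTI due to a ciprofloxacin non-susceptible organism".

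- Culture-positive: 250 − 50 = 200.
- Non-susceptible: 40/250 = 16% of those enrolled, or 40/200 = 20% of the culture-positive if all 40 are among them.
- Susceptible: 200 − 40 = 160.

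No assumed response rate, precision target, alpha or power is given, so the 40 is a bare expectation and there is no sample-size calculation to reproduce.

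**2. Precision of the single rate in 40 women** (exact Clopper-Pearson 95% intervals).

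| Responders | Rate | 95% CI |
|---|---|---|
| 12/40 | 30% | 16.6 to 46.5 |
| 20/40 | 50% | 33.8 to 66.2 |
| 28/40 | 70% | 53.5 to 83.4 |

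At 50% the half-width is (66.2 − 33.8)/2 = 16.2 points.

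**3. Dependence on the MIC mix.** Let s be the share of the 40 with low-level resistance, and p_low and p_high the response rates at low-level and high-level resistance. Then

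pooled rate = s × p_low + (1 − s) × p_high.

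Moving s from 25% to 75% shifts the pooled rate by 0.5 × (p_low − p_high). The documents give none of these quantities, so every rate below is an assumption.

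| p_low / p_high (assumed) | s = 25% | s = 50% | s = 75% | Shift, 25% to 75% |
|---|---|---|---|---|
| 70% / 30% | 40% | 50% | 60% | 20 points |
| 60% / 30% | 37.5% | 45% | 52.5% | 15 points |
| 50% / 40% | 42.5% | 45% | 47.5% | 5 points |
| 50% / 50% | 50% | 50% | 50% | 0 |

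Under the steepest gradient in the table, the mix moves the figure by more than the 16-point sampling half-width. Under a shallow gradient it hardly matters. A single pooled percentage would not show which case applies.

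**4. What MIC strata could show** (same assumed 70% and 30%).

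| Low / high split | Low-level | High-level |
|---|---|---|
| 20 / 20 | 14/20 = 70% (45.7 to 88.1) | 6/20 = 30% (11.9 to 54.3) |
| 10 / 30 | 7/10 = 70% (34.8 to 93.3) | 9/30 = 30% (14.7 to 49.4) |

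The intervals overlap in both splits. The numbers support description, not testing.

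**5. Do MICs exist?** Neither document says so directly. A category for rising MIC requires a baseline MIC, and the central laboratory's ceftriaxone rule looks like an MIC threshold, so baseline MICs very probably exist for many isolates. They may not exist for all. Protocol Appendix 2 has gram-negative pathogens tested locally only as appropriate, and a local report may give a category alone.

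**The case against.** **The study asks what proportion respond, not why.** A reader might infer from the rationale that the trial sets out to explain response despite resistance, and so must analyse MIC. The documents do not support that. The reasons are background, host factors are named beside PK/PD, and the stated gap is a proportion. A two-group rate goes most of the way to that narrower question. What remains is that the gap concerns resistant organisms, while the reported class is non-susceptible with no stated boundary.

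**Laboratory disagreement is not shown.** A reader might infer that central and local laboratories used different cut-offs, so that women with the same MIC were classed differently. The documents are silent on both cut-offs, and silence does not show a difference. Local results replace central ones only in defined circumstances, in an unknown number of women. The supportable statement is that a common cut-off is not assured.

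**The gradient is assumed.** This stands in full: the shift is zero if response does not vary with MIC.

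**The plan is descriptive and the group small.** SAP 7.6 rules out hypothesis testing, and 40 women spread over single doubling dilutions would leave few per cell. A regression of response on log2 MIC over all isolates would be driven largely by the 160 susceptible women. This argues for grouped dilutions and against making a regression a main deliverable, but not against showing the data.

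**The plan leaves room already.** Protocol 9.3 permits exploratory analyses and requires patient listings, and SAP 7.3 lists all isolates. None of these mentions MIC or commits to showing it beside response. The classes in SAP 7.1 may also be meant as columns for the efficacy tables, but the SAP does not say so.

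**Conclusion.** The point holds as a reporting gap that should be closed. No planned analysis shows response by baseline ciprofloxacin MIC. No ciprofloxacin cut-off is stated. The SAP's efficacy sections omit the susceptible versus non-susceptible response table that the protocol plans, while including one by ESBL.

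The consequence is conditional: if response varies with MIC, the rate in about 40 non-susceptible women reflects an unreported mix. On the assumed rates above, the effect is 0 to about 20 points for a low-level share between 25% and 75%; a gradient steeper than 70% versus 30% would give more. Protocol exclusion 10, which removes women whose available culture already shows ciprofloxacin resistance, may also alter the mix, in a way the documents do not quantify.

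It does not follow that any stated figure or the primary result is wrong, or that a steep gradient exists and is being concealed. The primary outcome in the whole m-MITT population does not use the susceptibility label.

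**What to change.** **SAP 5.3**
- List Day 12 overall, clinical and microbiologic response by ciprofloxacin-susceptible and non-susceptible, as the protocol plans.
- Add a descriptive table or listing of the same responses by baseline ciprofloxacin MIC in m-MITT and ME-TOC. Use grouped dilutions, take the highest MIC where two uropathogens are isolated, and include isolates with an MIC. State the number of women without one.
- Treat any regression on log2 MIC as optional and exploratory.

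**SAP 6.4**
- State one ciprofloxacin cut-off and apply it to every isolate with an MIC, whichever laboratory supplied it.

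**Cost.** SAP wording and an extra table in the style of the ESBL tables, with no new data where MICs are already held. The MIC table will have small cells and wide intervals, and women with only a local category report are left out of it, which is why their number should be shown.
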